## **Plan of Investigation**

### Design

This is an assessor-blinded, randomized controlled trial. A total of 248 eligible subjects will be recruited from local nursing and care homes. They will be randomly assigned to either an acupuncture group (named the “comprehensive acupuncture therapy [CAT]” group), an acupressure group (named the “Comfy Acupressure for the Elderly [CAE]” group), a combined acupuncture and acupressure group (named the CAT+CAE group), or a control group (named the routine care group), with 62 subjects per group. Subjects assigned to the CAT, CAE, and CAT+CAE groups will respectively receive 2 sessions of CAT, 3 sessions of CAE, and a combination of both per week for 12 weeks. The primary outcome is the baseline-to-endpoint change in score of the Montreal Cognitive Assessment

(MoCA). Secondary outcomes include various domains of MoCA, functional independence, psychological well-being, sleep quality, and level of pain. A generalized linear mixed-effect model will be used to compare outcomes over time among the four groups. This trial has been approved by the Institutional Review Board of the University of Hong Kong/Hospital Authority Hong Kong West Cluster (Ref No.: UW 19-821). The study protocol has been registered at ClinicalTrials.gov (NCT04305951) before enrolment. The trial will be conducted in compliance with the protocol, the ethical principles of the Declaration of Helsinki and its subsequent amendment. The study flow chart is shown in [Figure 1](#).

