## Subjects

### **Inclusion criteria**

Subjects will be eligible for this study if they: (a) are aged 65 years or above, (b) have a clinical diagnosis of any type of dementia or met the criteria of major and mild neurocognitive disorder based on the Fifth Edition of the Diagnostic and Statistical Manual of Mental Disorders (DSM-5); and (c) have mild to moderate dementia at a stage of 3 to 5 (Stage 3: mild cognitive decline; Stage 4: moderate cognitive decline/mild dementia; Stage 5: moderately severe cognitive decline/moderate dementia) on the Global Deterioration Scale.

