Fatal or life-threatening unexpected AEs will be reported to the regulatory bodies as soon as possible but no later than 7 calendar days after first knowledge by the principal investigator (PI) that a case qualifies, followed by as complete a report as possible within 8 additional calendar days. This report would include an assessment of the importance and implications of the findings, including relevant previous experience with the same or similar medicinal products. For other serious, unexpected AEs that are not fatal or life-threatening, they will be reported as soon as possible but no later than 15 calendar days after first knowledge by the PI or that the case meets the minimum criteria for expedited reporting. For non-serious AEs and serious AEs that are expected, they will be reported in a brief summary at the conclusion of the trial.

(d) Assessment schedule: Clinical assessment will be conducted at baseline, week 6, and week 12 (Table 3). For AEs, participants in active treatment groups will be asked whether they have experienced any AEs on each treatment and assessment session. Participants in the control group will be recorded for all AEs on a regular basis (baseline, 6, and 12 weeks).

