## **Data Management**

(a) Maintenance of consistency and fidelity: The study will last about 3 years and be carried out at multiple sites. There will also be many different professional investigators involved in the study. To ensure consistency and fidelity of intervention and assessment across sites and throughout a study period, training workshops will be conducted pre-trial and once per year thereafter. All investigators and caregivers will receive training. A training manual will be prepared for CAT and CAE procedures and clinical assessment instruments.

For intervention training, the PI and a senior CMP will instruct and demonstrate CAT and CAE. Trainees will practice CAT and CAE with each other. Investigators and caregivers who will perform CAT and CAE must obtain satisfactory training outcomes, which will be rated by the PI and a senior CMP.

For clinical assessment training, an investigator who has extensive experience in clinical assessment will instruct clinical instruments. An elderly person with dementia will be invited to be evaluated for MoCA by investigators who will be responsible for clinical assessment. An inter-rater reliability coefficient (k value) of >0.80 must be achieved after the completion of each training workshop.

To further ensure consistency and fidelity, the following additional measures will be taken: (1) all assessors will be deployed to each site via central allocation; (2) all assessments from baseline throughout the endpoint for each individual will be performed, if possible, by the same assessor who is blind to participants' interventions; and (3) all interventions of each patient will be conducted by the same investigator or caregiver, if possible.

(b) Safety assurance and ethical consideration: A Case Record Form (CRF) will be used to record each participant's treatment. Emergency contact numbers (the investigator's mobile number and a designated center staff member's mobile number) will be provided in the informed consent for

caregivers to report and seek advice in case of any AE. Paper copies of CRFs are stored in locked cabinets. Data will be entered using the double-entry strategy on password-protected computers.

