The study will be carried out in accordance with the ethical principles of the Declaration of Helsinki and its subsequent amendment, and ICH-GCP. This trial has been approved by the Institutional Review Board of the University of Hong Kong/Hospital Authority Hong Kong West Cluster (Ref No.: UW 19-821). The study protocol has been previously registered at ClinicalTrials.gov (NCT04305951) before enrolment. A full explanation of the study goal, procedures, and potential side effects and risks will be presented to each patient recruited. All participants are required to provide written consent. For those who cannot fully understand the study due to cognitive impairment, consent will be obtained from their guardians. Informed consent and other documents provided to patients will be written in both English and Chinese. This study is conducted on Chinese patients. Patients would not receive remuneration, but treatments and assessments directly associated with the clinical trial will be provided at no cost. The issue of confidentiality is a major ethical issue, and will be solved by recording the data in a manner that does not allow the participants to be identified (i.e., using a non-recognizable code for each patient). A review of medical records that have already been recorded as part of clinical care. Therefore, this poses no physical risks.

(c) Record retention: The PI, research team, and ethical review authority are responsible for overseeing this study to get access to, use, and retain subjects' personal data for the purposes of clinical study, and the relevant regulatory bodies can get access to subjects' personal data for the purposes of checking and verifying the integrity of study data and assessing compliance with the study protocol and relevant requirements. All collected data will be secured in compliance with the Hong Kong Personal Data (Privacy) Ordinance (CAP 486). The collected personal information and study data will be kept for 3 years after the completion of the study.

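### Adverse events are actively sought only by asking cognitively impaired participants in the active arms, and the control arm's source is unnamed, so events can be missed and the four-arm safety comparison rests on unequal ascertainment

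*Protocol*

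**What the plan says.** Protocol, Assessment (d), sets two rules for finding AEs. In the three active arms, "participants in active treatment groups will be asked whether they have experienced any AEs on each treatment and assessment session". For routine care, "Participants in the control group will be recorded for all AEs on a regular basis (baseline, 6, and 12 weeks"), with no statement of who supplies the information. Assessment (c), repeated in the SAP under Safety outcomes, adds that AEs are recorded systematically at each visit with onset date and time, duration, severity and relationship. It names no source either. Independent evaluation by staff who do not assess outcomes is planned, but it applies to events already found.

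The participants must "have mild to moderate dementia at a stage of 3 to 5" on the Global Deterioration Scale, where the top of the range is "Stage 5: moderately severe cognitive decline/moderate dementia". Data Management (b) provides that "For those who cannot fully understand the study due to cognitive impairment, consent will be obtained from their guardians".

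Two other places come near a second source, both in Data Management (b). Emergency numbers are supplied in the consent form for "caregivers to report and seek advice in case of any AE". Later there is an incomplete sentence, "A review of medical records that have already been recorded as part of clinical care", set among remarks on confidentiality and risk.

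Safety is aim 3 of the Protocol. SAP Proposed Table 4 lists treatment-related AEs in the active arms without tests. Proposed Table 5 counts patients with AEs by severity in all four arms, with a chi-square or Fisher test across them.

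**The concern.** The one explicit method of seeking AEs relies on the memory and communication of people enrolled because these are impaired. The Protocol's own introduction describes progressive memory loss and growing difficulty in communication in this population. The setting offers a better-placed informant: "A total of 248 eligible subjects will be recruited from local nursing and care homes", where staff can observe the residents. Yet no one is scheduled to ask them.

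Two things are at stake. First, absolute AE proportions, which a reader will use to judge safety, may be too low for events that only the participant would notice, and onset and duration may be unreliable. Expedited reporting and discontinuation for an AE also depend on the event becoming known. Second, Table 5 compares arms whose events were found in different ways, so a difference, or its absence, may reflect ascertainment and not treatment.

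**Working it through.** **1. Ascertainment by arm.** Session schedules are from Protocol, Treatment procedure (b) to (d); AE rules are from Assessment (d).

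| Arm | Stated AE source | Treatment sessions | Average gap between AE contacts |
|---|---|---|---|
| CAT | participant is asked | 24 (2 per week) | 7/2 = 3.5 days |
| CAE | participant is asked | 36 (3 per week) | 7/3 = 2.3 days |
| CAT+CAE | participant is asked | 24 + 36 = 60, if given separately | no longer than for CAE |
| Routine care | not stated | none | 6 weeks = 42 days |

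After baseline, control has two AE contacts; the active arms have at least 24 treatment contacts plus the assessments.

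**2. Is there another planned source?** The caregiver line works only if a caregiver decides to call, so it is passive. The record-review fragment states no purpose, timing or link to AEs, so it cannot be counted as a planned check. No other section names an AE source.

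**3. Which events depend on recall?** Bleeding and hematoma in Table 4 can be seen by the practitioner. Hospitalization through aggravation of the condition leads to discontinuation (Treatment procedure (f)), and serious AEs and deaths are listed separately in the SAP, so these depend little on recall. What remains is mainly mild and moderate events that arise between sessions, such as later dizziness, headache or pain, and events unrelated to needling. All of these belong in Table 5.

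**4. Size.** The plan's figure of 62 per arm reproduces: 2/(2.1/3.6)² × 7.9 = 46.4, and 46.4/0.75 = 61.9. It is derived for MoCA and says nothing about AEs. No AE rate or capture share is given, so no undercount can be derived.

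**5. Illustration of unequal capture; every rate is an assumption.** Let p be the true proportion of patients with at least one AE, equal in all arms. Let c be the proportion of those patients in whom an AE is recorded. The observed proportion is p × c. With a and b the observed proportions in one active arm and control, m = (a + b)/2 and n = 62, the chance of a significant pairwise excess in the active arm is about

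Φ{ [ (a − b) − 1.96 √(2m(1 − m)/n) ] / √( [a(1 − a) + b(1 − b)]/n ) }.

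For p = 0.30, c = 0.90 active and 0.50 control: a = 0.27, b = 0.15, m = 0.21. This gives (0.120 − 1.96 × 0.0732)/0.0724 = −0.32, and Φ(−0.32) = 37%.

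| True p | Capture 90% v 70% | Capture 90% v 50% |
|---|---|---|
| 20% | 9% | 25% |
| 30% | 12% | 37% |
| 40% | 16% | 51% |

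The planned test is across four groups. Simulating 200,000 trials per setting, with 90% capture in all three active arms, the Pearson chi-square test on 3 degrees of freedom rejects in 8%, 10% and 14% (70% in control) and 20%, 33% and 49% (50% in control). The nominal level is 5%.

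**The case against.** Several things can fairly be said for the plan.

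- **Recall in the active arms is short**, about 2 to 4 days, and practitioners see several of the listed reactions. This stands, and it confines the problem to events between sessions that the practitioner does not see.
- **Self-report is documented for the active arms only.** This stands. Staff or records may be the control source in practice, but the plan does not say so.
- **The caregiver line covers any AE, not only emergencies, and a record review is mentioned.** Both are true, but neither is a scheduled AE enquiry.
- **An undercount is inferred, not shown.** This stands. A reader might go further and conclude that AEs will be forgotten in a calculable share of participants. The documents give no recall rate, and an assumed per-event rate does not carry over to Table 5, which counts patients. A patient with two AEs, each recalled independently with probability 0.40, is still counted with probability 1 − 0.60² = 0.64; with 0.80 it is 1 − 0.20² = 0.96.
- **The bias may not favour treatment.** A reader might infer that the active arms will look falsely safe in Table 5. The contact schedule points the other way: control is contacted least and is probably under-recorded most, which would make the active arms look worse by comparison. Concern about rates that are too low in the active arms applies to the absolute figures only.

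**Conclusion.** The concern holds in a limited form. The only active elicitation stated is to ask active-arm participants, whose decline ranges up to stage 5. The control arm has a sparser schedule and no named source. Some mild and moderate events can be missed, and their onset and duration may be unreliable. Absolute AE proportions may therefore be too low, and the Table 5 comparison may be biased, probably through greater under-recording in control. That direction assumes that control participants are also the informants, over about 42 days; if staff or records supply control AEs, it could differ.

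The size is unknown. The 8% to 51% rejection rates above show only that plausible differences in capture could move the test well away from 5%; they do not estimate what will happen. Deaths and hospitalizations are little affected. The documents do not support saying that events will be forgotten, or that the trial would call the treatments safe for that reason. The gap should still be closed, because it bears on a stated aim and the remedy uses visits and staff already in the plan.

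**What to change.** - **Protocol, Assessment (c) and (d):** state that at week 6 and week 12, in all four arms, AE staff who do not assess outcomes will put one standard AE question, covering the preceding 6 weeks, to the duty nurse or main caregiver. They will also check the home's incident or transfer records where these are kept and consent allows.
- **SAP, Safety outcomes:** state that the between-group test in Table 5 uses this common source. Keep participant reports at sessions as an additional source, tabulated separately for the active arms (Table 4).
- **Protocol, Data Management (b):** complete the sentence on medical-record review, saying what is reviewed, when, and whether it serves AE ascertainment.

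**Cost:** up to 248 × 2 = 496 short enquiries at visits already scheduled, one added form page, and consent wording for care-home records. The documents do not say which records the homes keep, so the staff question must be able to stand alone. More AEs will probably be reported. One limit remains: treatment is given in the homes, so staff may know the allocation. A common question and interval make the source and schedule equal across arms but do not blind the informant.

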The GDS-15 consists of 15 questions in which subjects are asked to respond by answering yes or no in reference to how they felt over the past week. Of the 15 items, 5 items (question numbers 1, 5, 7, 11, 13) indicate depression when answered negatively, while the rest (question numbers 2, 3, 4, 6, 8, 9, 10, 12, 14, 15) indicate the presence of depression when answered positively. The GDS-15 score is interpreted as follows: normal (0-4), mild depression (5-8), moderate depression (9-11), and severe depression (12-15). GDS can be used in mild to moderately cognitively impaired older adults. ISI is a

validated 7-item scale to assess the severity of insomnia. The total score ranges from 0 to 28, with scores of 0-7 indicating no clinically significant insomnia, 8-14 indicating subthreshold insomnia, 15-21 indicating moderate insomnia, and 22-28 indicating severe insomnia. Depressive and sleep symptoms are investigated because elderly people with cognitive impairment often have comorbid emotional and sleep disorders. The benefits of acupuncture and acupressure for depression and insomnia have been confirmed in our previous studies.

(c) Adverse events: The severity of adverse events (AEs) will be assessed according to the Common Terminology Criteria for Adverse Events (CTCAE) v5.0 criteria. AEs will be systematically recorded, in which AEs that first appear in the study or worsen relative to the pre-study status will be recorded at each visit, including the date and time of onset, duration, severity, relationship to intervention, and action taken accordingly. All possible events will be independently evaluated by staff who do not assess treatment outcomes. The causality between treatment procedures and AEs will be assessed.

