### **Data processing and analysis**

One biostatistician who is blinded to interventions will be responsible for statistical analysis. The analysis will be carried out on the intention-to-treat (ITT) population, for which participants have been randomized. A linear mixed-effect model will be applied to compare the primary outcome (changes in total MoCA score from baseline) and secondary outcomes (changes in scores of the Digit span test, MBI, VAS, GDS and ISI), with time (baseline, week 6, and week 12) and group (CAT, CAE, CAT+CAE, and routine care) as categorical fixed factors and random intercepts within a scaled identity covariance matrix. Gender, age, baseline MoCA score, and baseline medication will serve as covariates. Subgroup analysis will be further conducted to compare outcomes by gender, age, and severity of dementia to detect whether these factors are associated with the outcomes. Pairwise comparisons will be further carried out to examine between-group differences. One-way analysis of variance (one-way ANOVA) will be used to detect differences in continuous baseline variables. Categorical baseline variables, including discontinuation and incidence of AEs, will be analyzed using the Chi-square test or Fisher's exact test. Statistical significance was defined as a two-tailed  $P < 0.05$ . The analysis will be conducted using R Studio software.

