- (c) severity of dementia (mild cognitive decline [Stage 3], moderate cognitive decline [Stage 4], moderately severe cognitive decline [Stage 5])

Secondary outcomes

A linear mixed-effect model will be applied to compare the secondary outcomes, including changes in scores of the Digit span test (DSF and DSR), MBI, VAS, GDS and ISI, with time (baseline, week 6, and week 12) and group (CAT, CAE, CAT+CAE, and routine care) as categorical fixed factors and random intercepts within a scaled identity covariance matrix. Gender, age, baseline MoCA score, and baseline medication will serve as covariates.

Pairwise comparisons will be further carried out to examine between-group differences. Two-tailed P-values will be reported in addition to confidence intervals ([Proposed Tables 2 and 3](#)).

Safety outcomes

AEs related to treatment will be tabulated by treatment group without statistical tests or confidence intervals ([Proposed Table 4](#)).

All AEs that occurred throughout the trial will be tabulated by treatment group and AE category (mild, moderate, severe, life-threatening, or death). Chi-square test or Fisher's exact test will be used to detect differences between the four groups ([Proposed Table 5](#)).

Details of serious AEs and death cases will be summarized and listed in a separate table.

Interim analysis

No interim outcome analyses were done prior to the completion of the study to avoid assessment bias.

Missing data

A linear mixed-effect model will be conducted for all analyses of primary and secondary outcomes without imputation of missing data.¹⁶

Proposed Tables

Table 1. Baseline characteristics

Characteristic	CAT (n=62)	CAE (n=62)	CAT+CAE (n=62)	Routine care (n=62)	Total (n=248)	P value
Age, years *	XX ± XX	XX ± XX	XX ± XX	XX ± XX	XX ± XX	XX
Gender (Female) †	XX (XX)	XX (XX)	XX (XX)	XX (XX)	XX (XX)	XX
Marital status †						XX
Married or living with partner	XX (XX)	XX (XX)	XX (XX)	XX (XX)	XX (XX)	
Single, separated, divorced, or widowed	XX (XX)	XX (XX)	XX (XX)	XX (XX)	XX (XX)	
Education level †						XX
Uneducated	XX (XX)	XX (XX)	XX (XX)	XX (XX)	XX (XX)	
Primary or below	XX (XX)	XX (XX)	XX (XX)	XX (XX)	XX (XX)	
Lower Secondary	XX (XX)	XX (XX)	XX (XX)	XX (XX)	XX (XX)	
Upper Secondary	XX (XX)	XX (XX)	XX (XX)	XX (XX)	XX (XX)	
University or above	XX (XX)	XX (XX)	XX (XX)	XX (XX)	XX (XX)	
Past occupation †						XX
Managers and administrators	XX (XX)	XX (XX)	XX (XX)	XX (XX)	XX (XX)	

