‡ P value was calculated using a mixed-effects model with baseline adjustment to illustrate pre- and post-treatment within-group differences. Those which statistical differences $p<0.05$ reached significance level are indicated in bold font

Table 4. Adverse events related to treatment, n (%)^{*}

Adverse event	CAT (n = 62)	CAE (n = 62)	CAT+CAE (n = 62)
Bleeding at the site of needling	XX (XX)	XX (XX)	XX (XX)
Hematoma around the site of needling	XX (XX)	XX (XX)	XX (XX)
Dizziness after treatment	XX (XX)	XX (XX)	XX (XX)
Headache after treatment	XX (XX)	XX (XX)	XX (XX)
Localized pain	XX (XX)	XX (XX)	XX (XX)
Needle phobia	XX (XX)	XX (XX)	XX (XX)

Abbreviations: CAT, comprehensive acupuncture therapy; CAE, Comfy Acupressure for the Elderly.

* Data was expressed as number of patients (%).

Table 5. Reported adverse events in different categories, n (%)^{*}

Adverse Event Category	CAT (n=62)	CAE (n=62)	CAT+CAE (n=62)	Routine care (n=62)	P-value*
Any	XX (XX)	XX (XX)	XX (XX)	XX (XX)	XX
Mild	XX (XX)	XX (XX)	XX (XX)	XX (XX)	XX
Moderate	XX (XX)	XX (XX)	XX (XX)	XX (XX)	XX
Severe	XX (XX)	XX (XX)	XX (XX)	XX (XX)	XX
Life-threatening	XX (XX)	XX (XX)	XX (XX)	XX (XX)	XX
Death	XX (XX)	XX (XX)	XX (XX)	XX (XX)	XX

Abbreviations: CAT, comprehensive acupuncture therapy; CAE, Comfy Acupressure for the Elderly.

* Data was expressed as number of patients (%). Those which statistical differences $p < 0.05$ reached significance level are indicated in bold font.

[figure not shown]

Figure 1. CONSORT Flowchart

References

1. American Psychiatric Pub. Diagnostic and Statistical Manual of Mental Disorders (DSM-5®). American Psychiatric Pub; 2013.

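### Adverse events are sought at every session in the active arms but recorded only at weeks 6 and 12 in routine care, yet the SAP tests all events across the four arms

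*Protocol*

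**What the plan says.** Protocol, Assessment, item (d), gives the collection schedule. In the three treated arms, "participants in active treatment groups will be asked whether they have experienced any AEs on each treatment and assessment session". For the comparator, "Participants in the control group will be recorded for all AEs on a regular basis (baseline, 6, and 12 weeks"). Item (c) of the same section adds that "AEs that first appear in the study or worsen relative to the pre-study status will be recorded at each visit", and the number of visits differs by arm.

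The SAP's analysis section on safety outcomes handles two sets of events differently:

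- Treatment-related events (Proposed Table 4, active arms only): "AEs related to treatment will be tabulated by treatment group without statistical tests or confidence intervals".
- All events (Proposed Table 5, headed "Reported adverse events in different categories"): "All AEs that occurred throughout the trial will be tabulated by treatment group and AE category (mild, moderate, severe, life-threatening, or death"). Here "Chi-square test or Fisher's exact test will be used to detect differences between the four groups". The table has a routine-care column and a P-value column, with P<0.05 in bold.

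Protocol, Data processing and analysis, also provides a test: "Categorical baseline variables, including discontinuation and incidence of AEs, will be analyzed using the Chi-square test or Fisher's exact test". It does not say whether this means all AEs or all four arms.

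**The concern.** A between-arm test of AE incidence is interpretable only if an event of a given kind has a similar chance of being recorded in each arm. Here the chance probably differs by design. Brief, mild events are easier to pick up when someone asks several times a week than when they are recorded at six-week intervals in people with cognitive impairment. The source of routine-care entries (participant, staff or records) is not stated.

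Safety is the third aim of the trial, and Table 5 is the only safety table with a between-arm test. A bold P value on the Any row could be read as harm from acupuncture or acupressure when it reflects the frequency of asking. Conversely, a null result could hide a true reduction. Serious AEs and deaths are listed separately and treatment-related events are not tested, so the problem is confined to P values on rows with common events.

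**Working it through.** **1. Recording occasions after baseline.** Inputs: 24 CAT sessions and 36 CAE sessions (Protocol, Treatment procedure), plus assessments at weeks 6 and 12.

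- CAT: 24 + 2 = 26
- CAE: 36 + 2 = 38
- CAT+CAE: 24 + 36 + 2 = up to 62. The sum of 60 sessions is derived, not stated. If every CAT session shared a day with a CAE session, the count would be 36 + 2 = 38.
- Routine care: 2

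The ratio to routine care runs from 26/2 = 13 to 62/2 = 31.

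**2. Does anything equalise capture?** Recording at each visit reproduces the imbalance. The emergency number in Protocol, Data Management (b), is open to all arms but depends on caregivers calling. The sentence on medical-record review in the same section is a fragment that is not tied to AEs. Independent evaluation of events applies only to events already recorded.

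**3. Number per arm for the test.** The plan's own figure reproduces: 2/(2.1/3.6)² × 7.9 = 46.4, and 46.4/0.75 = 61.9, so 62 per arm.

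**4. Effect on the test, for illustration.** Assumptions: the same true 12-week risk p of at least one event in every arm, 62 analysed per arm, and a four-group chi-square (3 df) at 0.05. Table 5 counts patients, so if a fraction c of events is captured, the recorded risk is 1 − (1 − p)^c. For example, with p = 0.30 and c = 0.65, this is 1 − 0.70^0.65 = 0.207 in routine care against 0.30 in the active arms.

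Simulated probability of P<0.05 (300,000 runs per cell), with full capture in the active arms:

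| True risk | Control capture 100% | 80% | 65% | 50% |
|---|---|---|---|---|
| 5% | 4.3% | 4.8% | 5.7% | 7.3% |
| 10% | 4.8% | 5.9% | 8.3% | 12.8% |
| 20% | 4.9% | 7.3% | 13.3% | 25.6% |
| 30% | 5.0% | 8.7% | 19.0% | 40.3% |

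At 30% risk and 65% capture, routine care lies below the active-arm mean in almost all rejections (0.187 of 0.189), so the error nearly always looks like harm from treatment.

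**5. Sensitivity.**

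- *Active arms also lose 10% of events* (missed, or shorter observation), 30% risk: 6.0%, 12.1% and 28.2% at control capture of 80%, 65% and 50%.
- *Routine care complete, active arms lose 10%*, 30% risk: 5.9%, with the bias reversed.
- *Simpler model, recorded risk = p × c* (20,000 runs), control capture 75%, 50% and 25%: at 10% risk 7%, 13% and 30%; at 30% risk 13%, 49% and 93%.
- *Rare rows*, true risk 1% to 2%, Fisher's exact test: below 3% even at 25% capture.

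**The case against.** The strongest reply is that two recording dates are not two chances of detection. The protocol says routine care is recorded for all AEs, not that participants are asked only twice. Onset date and duration are to be noted, so a week-6 entry can cover the whole interval. Participants live in or attend care homes, where staff may notice events, and caregivers in any arm can telephone. Active-arm observation may also be shorter, because intolerance of treatment is a reason for discontinuation that can arise only there. All of this stands as a limit on size and direction: the 13- to 31-fold contrast in occasions is not a contrast in capture, and the bias could be small or reversed. It does not restore comparability, because staff notes or records would still be a different method from asking at each session.

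A second reply is that large inflation needs both a common event and poor control capture, and that the likelier error makes treatment look less safe, not safer. Both points are correct. The simulation also gives the three active arms equal capture, although their numbers of contacts differ.

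A third is that removing P values leaves the counts just as unequal. That is true, which is why disclosure must accompany the removal. The Moderate row might turn out to be rare, but that is not known in advance, and the choice of rows should be fixed before the data are seen.

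**Conclusion.** The concern holds. Both the unequal collection and the four-arm test of all AEs are stated in the documents, and nothing in them reconciles the two. More complete recording in the active arms is likely but not certain.

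The size cannot be derived from the documents. Under the assumptions shown, inflation is material only where a row is common and control capture is well below active capture: about 19% at 30% risk with 65% capture, but only about 8% at 10% risk with the same capture. It is absent if capture is equal. Rows for rare events are little affected, Table 4 and the separate listing of serious AEs and deaths are not at issue, and the MoCA analysis is unaffected. The change should be made, but it concerns the reading of one safety table and not the conduct or main result of the trial.

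**What to change.** Keep the session-by-session questioning and every count in Table 5. Then:

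1. In the SAP safety analysis and Table 5, remove the P values from the Any, Mild and Moderate rows.
2. State in the SAP and the report that ascertainment differed by arm (every treatment session against weeks 6 and 12), and that fuller recording in the active arms is likely but not certain.
3. Amend Protocol, Data processing and analysis, so that AE incidence is tested only for the rows that keep a P value.
4. State in Protocol, Assessment (d), where routine-care AE entries come from, and whether the record review mentioned under Data Management is used for AEs.

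These four items need only wording. The price is the loss of a formal test on the common-event rows, which matches how the SAP already treats Table 4.

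Optional: record on the CRF the contact at which each AE was elicited, and add a supplementary comparison limited to events elicited by one standard question at weeks 6 and 12 in all four arms. This costs one CRF field and one question at two existing visits. It would miss transient session events, rely on six-week recall in people with cognitive impairment and lean towards no difference, so it should be read only beside the full descriptive table.
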